4.11.3 Additional Efficacy Analyses

Intraocular Pressure

All analyses performed for IOP in the study eye will be repeated for the fellow eye.

4.12 Safety Analyses

All safety analyses will be performed in the Safety population. Missing data will not be imputed.

4.12.1 Adverse Events

Treatment-emergent adverse events (TEAE) are defined as AEs starting on or after the first dose of IP. A pre-existing event that worsens in severity after receiving the first dose of IP is treated as a new TEAE with date of onset set to the date of the increased severity. Summary tables will include TEAEs only. TEAEs will be summarized by treatment and overall. Non-treatment emergent AEs will be listed only.

An ocular event is an event where the site of the event is reported as both eyes (OU), right eye (OD) or left eye (OS).

Proportion of subjects reporting an event will be calculated based on the number of subjects in the corresponding treatment group. The 95% CI will be calculated using the Clopper-Pearson method.

The number and percentage of subjects reporting any event, any non-ocular event, and any ocular event will be summarized.

An overall summary table of TEAE will be provided by treatment group and location (non-ocular and ocular) for the following categories:

Confidential

- Number and percentage of subjects with a TEAE
- Number and percentage of subjects with a treatment-related TEAE
- Number and percentage of subjects with a TEAE leading to IP discontinuation
- Number and percentage of subjects with a TEAE leading to study discontinuation
- Number and percentage of subjects with a serious TEAE
- Number and percentage of subjects with a treatment-related serious TEAE
- Number and percentage of subjects with a TEAE leading to death

AEs will be coded using Medical Dictionary for Regulatory Activities (MedDRA) version 26 or higher. The following summaries will be provided:

- TEAEs by System Organ Class (SOC) and Preferred Term (PT)
- Serious TEAEs by SOC and PT
- TEAEs leading to IP discontinuation by SOC and PT
- TEAEs leading to study discontinuation by SOC and PT
- TEAE leading to death by SOC and PT
- TEAEs by SOC, PT, and maximum severity
- Treatment-related TEAEs by SOC and PT

In the above summaries, when multiple events of the same SOC or PT are reported, subjects are counted only once under each SOC and PT. If a subject has the same AE on multiple occasions, the highest severity (severe, moderate, mild) recorded for the event will be presented. Missing severity will be considered as severe. Events reported as definitely, probably or possible related to IP and events with a missing relationship will be considered as related to IP. The above summaries will be ordered by overall descending frequency of SOC and then, within a SOC, by overall descending frequency of PT.

In addition, listings for SAEs, deaths, and AEs leading to IP discontinuation will be provided.

4.12.2 Vital Signs

Heart rate and blood pressure (systolic and diastolic), and change from baseline, will be summarized by treatment group, visit and timepoint.

4.12.3 Best-corrected Visual Acuity

Best-corrected visual acuity (BCVA) and change from Baseline in BCVA will be summarized in the logMAR scale by eye (study eye and fellow eye), visit and treatment group.

In addition, categorical summaries of change from Baseline in BCVA will be generated. The number and percentage of subjects with >2 lines loss, >1-2 lines loss, 0-1 line loss, >0 to 1 line gain, >1 to 2 lines gain and >2 lines gain will be summarized by eye (study eye and fellow eye), visit and treatment group.

4.12.4 Slit Lamp Biomicroscopy

The number and percentage of subjects within each category of slit lamp examinations will be summarized by treatment group, visit, timepoint and eye (study eye and fellow eye).

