1.2 Preclinical and Human Data

For complete information on the preclinical studies performed, please see the Investigator's Brochure.

H1337, in the first human trial (ALY337-201) was generally well tolerated. Instillation site pain, instillation site erythema, and vision blurred were reported, usually mild in severity without an apparent dose-response.; instillation site erythema, blurred vision, and muscle strain were reported in 3 subjects at moderated intensity.

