7. ASSESSMENT OF SAFETY

7.1 Adverse Event Reporting

The investigator is responsible for monitoring the safety of subjects who have entered the study. Subjects should be asked at each visit about any changes in their health status. Any changes in health status after informed consent has been obtained, but prior to the first dose of IP, will be reported as medical history. Changes will be reported as AEs after the subject receives the first dose of IP (Day 1). Ongoing AEs at study completion (Day 28) or the final study visit will be followed until the event resolves, stabilizes, or for 30 days, whichever comes first.

All adverse events (serious and non-serious) must be documented regardless of the causal relationship to the study medication. The severity, frequency, seriousness, duration, relationship to IP(s), treatment of event, action taken with IP, and outcome for every adverse event should be documented.

Non-clinically significant incremental < 2 unit grade changes in conjunctival hyperemia (according to the photographic reference scale provided for the trial) are not required to be reported as adverse events; changes ≥2 unit grade changes must be reported as an Adverse Event and tracked until returning to baseline.

To capture the most potentially relevant safety information during a clinical study, it is important that investigators record accurate AE terms. Wherever possible, a specific disease or syndrome rather than individual associated signs and symptoms should be identified by the investigator and recorded. However, if an observed or reported sign or symptom is not considered a component of a specific disease or syndrome by the investigator, it should be recorded as a separate AE.

Investigators are required to report to D. Western Therapeutics, Inc. or its representative all observed and/or volunteered AEs occurring during the clinical trial (21 CFR §312.64[b]) regardless of treatment group or suspected causality to the investigational drug.

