2.2 Secondary Objective

The secondary objective of this study is to evaluate the local ocular and systemic safety of 3 dose regimens of H-1337.

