4.1 Definitions and Conventions

Listings present the subjects individual data, while summary tables present the summary statistics of subjects data.

Summary statistics will be presented for continuous variables, by way of n, mean, standard deviation (SD), median, minimum and maximum. For categorical variables including binary variables, frequency counts and percentages will be presented. Percentages will be calculated using the total number of subjects per treatment groups or the total number of subjects with an assessment per treatment groups, depending on the nature of the analysis.

In addition, 95% 2-sided confidence intervals (CIs) will be presented, where relevant. In case of percentages, the CI will be computed using the Clopper-Pearson method. The CI will be computed for continuous variables using a t-test analysis.

Summary statistics will be displayed by treatment groups, which will be labelled as follow:

- Group 1: H-1337 0.6%
- Group 2: H-1337 1.0% b.i.d
- Group 3: H-1337 1.0% q.a.m
- Group 4: Timolol 0.5%

Baseline Value is defined as the last non-missing value prior to the first IP administration for vital signs, BCVA, biomicroscopy and dilated ophthalmoscopy (Day 1 Pre- T_0 for vital signs, BCVA and biomicroscopy; Screening for dilated ophthalmoscopy). For IOP and conjunctival hyperemia grading, time-matched baseline values are defined at Pre- T_0 on Day 1 (Visit 3), T_0 +2 hours, T_0 +4 hours, T_0 +8 hours and T_0 +12 hours on Day 0 (Visit 2). For mean diurnal IOP, baseline is defined at Day 0.

Change from Baseline is defined as the difference in value of the assessment between the considered visit and the baseline value. In the case of IOP and conjunctival hyperemia grading, change from Baseline is the difference in value of the assessment between the considered visit at a particular timepoint and the corresponding baseline value.

Study eye is defined as the eye that meets all entry criteria including the IOP criteria after washout. Should both eyes meet the criteria then the study eye will be the eye with the higher 8 am IOP at Baseline (Day 1). If both eyes have the same 8 am IOP at Baseline (Day 1), the study eye will be the right eye.

SAS® version 9.4 or above will be used to perform the analyses.

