4.12.5 Conjunctival Hyperemia Grading

The number and percentage of subjects within each grading category will be summarized by treatment group, visit, timepoint and eye. In addition, shift from baseline will be summarized by treatment group, visit, timepoint and eye (study eye and fellow eye).

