4.12.6 Dilated Ophthalmoscopy

The number and percentage of subjects within each assessment category will be summarized by treatment group, visit and eye (study eye and fellow eye).

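### The planned slit-lamp and hyperemia tables cannot count, per subject, who worsened from baseline or who ever reached a given grade

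*SAP*

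**What the plan says.** Safety is a stated objective in its own right (SAP 2.2): "The secondary objective of this study is to evaluate the local ocular and systemic safety of 3 dose regimens of H-1337". The three graded eye examinations are handled as follows.

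- Slit lamp (SAP 4.12.4): "The number and percentage of subjects within each category of slit lamp examinations will be summarized by treatment group, visit, timepoint and eye". No change or shift is mentioned.
- Hyperemia (SAP 4.12.5): "The number and percentage of subjects within each grading category will be summarized by treatment group, visit, timepoint and eye". A further sentence adds: "In addition, shift from baseline will be summarized by treatment group, visit, timepoint and eye".
- Fundus (SAP 4.12.6): "The number and percentage of subjects within each assessment category will be summarized by treatment group, visit and eye". Again there is no shift.

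SAP 4.1 nevertheless sets a baseline for two of these: "Baseline Value is defined as the last non-missing value prior to the first IP administration for vital signs, BCVA, biomicroscopy and dilated ophthalmoscopy". For hyperemia it sets time-matched baselines, Pre-T0 from Day 1 and the later clock times from Day 0.

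Protocol 8.2 says that summary tables show observed values and change from baseline, and that shift tables are optional for selected safety measures. The SAP takes precedence over the protocol (SAP 1). Its list of changes (SAP 5) does not mention dropping the change from baseline for these examinations.

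On adverse events, Protocol 7.1 makes hyperemia changes of 2 units or more reportable and exempts the following: "Non-clinically significant incremental < 2 unit grade changes in conjunctival hyperemia".

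**The concern.** The trial compares three regimens and introduces 1.0%, above the highest concentration in the previous study (0.6%, Protocol 1.4). Two basic tolerability questions are how many subjects per regimen worsened on slit lamp, and how many ever reached a given grade of redness.

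The first needs a within-subject comparison. Exclusion 15 accepts mild blepharitis and prostaglandin-related hyperemia, so a baseline grade need not be zero. Equal counts before and after treatment could mean that nobody changed, or that some eyes worsened while others improved.

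The second needs one value per subject across readings. A shift table at each time point describes each reading correctly, but it does not say whether the affected subjects at +2 h on Day 1 and at +4 h on Day 28 are the same people.

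The neighbouring sections do use their baselines: vital signs (4.12.2) and BCVA (4.12.3) are summarized as change, and hyperemia as shift. Per-subject worst values are also already in the plan, since TEAEs are tabulated by maximum severity (4.12.1). Slit lamp and fundus are the exceptions on change from baseline.

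**Working it through.** The documents state no figure on this point, so there is none to reproduce. The prevalences and correlations below are assumptions, used only to show what the planned tables leave undetermined.

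**1. Slit lamp: what two marginal counts allow.** Take n = 50 per arm (Protocol 3.1), b eyes with a finding at baseline and f at Day 28. The number of newly affected eyes lies between max(0, f − b) and min(f, n − b).

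- b = 10, f = 10: from max(0, 0) = 0 to min(10, 40) = 10, that is 0% to 20% of the arm.
- b = 5, f = 10: from max(0, 5) = 5 to min(10, 45) = 10, that is 10% to 20%.

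A shift table replaces each range with one number.

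**2. Hyperemia: number of readings.** Protocol Table 1, without the optional +12 h, gives Day 1 at +2, +4 and +8 h (3), Day 14 at Pre-T0 (1), and Day 28 at Pre-T0, +2, +4 and +8 h (4). The total is 3 + 1 + 4 = 8. With +12 h on Days 1 and 28 it is 10.

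**3. Hyperemia: share ever affected.** Let p be the share with a given grade at each of k = 8 readings. If it is always the same subjects, the share ever affected is p. If readings are independent, it is 1 − (1 − p)^8. If no subject is affected twice, it is min(1, 8p). The middle column uses an exchangeable latent-normal model with correlation 0.5.

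| p (assumed) | same subjects | correlation 0.5 | independent | never twice |
|---|---|---|---|---|
| 5% | 5% | 22% | 34% | 40% |
| 10% | 10% | 37% | 57% | 80% |
| 20% | 20% | 58% | 83% | 100% |

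For p = 10%, 1 − 0.9^8 = 1 − 0.430 = 0.570. At correlations 0.7 and 0.9 the share is 29% and 20%. The percentages at each time point are identical across a row, so the planned counts cannot separate these cases. The planned shift at each time point does not link one reading to another either.

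**4. Which rises must be reported as AEs.** The scale is 0, 0.5, 1, 2, 3 (Protocol 5). Rises of at least 2 units are 0 to 2 (2), 0 to 3 (3), 0.5 to 3 (2.5) and 1 to 3 (2). Rises that end at moderate yet fall short are 0.5 to 2 (1.5) and 1 to 2 (1). If judged not clinically significant, these need not enter the AE tables.

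**5. Slit-lamp grades.** Protocol 5 grades lid erythema and edema, conjunctival and corneal edema, cells and flare. Unlike hyperemia, none of these has a grade change that makes an AE report mandatory. Reporting rests on clinical significance (Protocol 7.2).

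**The case against.** The strongest reply is that per-subject local toxicity is already reported through ocular TEAEs, which the protocol synopsis names as the safety endpoint. SAP 4.12.1 tabulates them by SOC, PT and maximum severity. Hyperemia rises of 2 or more units must be AEs, so a subject starting at grade 0 who reaches moderate redness is captured. New or worse fundus findings after the first dose are AEs (Protocol 5, Dilated Ophthalmoscopy). This stands, and it confines the gap to graded changes that do not become AEs.

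Four stronger readings are tempting, and the documents do not support them.

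- *Local toxicity is hidden.* The AE route just described and the planned hyperemia shift contradict this.
- *An arm that loses subjects to redness looks better at Day 28.* The Day 28 table alone could mislead, but such losses would appear under TEAEs leading to IP or study discontinuation (4.12.1) and among withdrawal reasons (4.4). SAP 4.1 also leaves the denominator open.
- *Early Termination grades are left out.* SAP 3.2 lists six scheduled visits, but the SAP is silent on where other readings go. Exclusion is an inference.
- *Redness is an established harm of H-1337.* Protocol 1 reports a relatively low incidence of hyperemia. Protocol 1.2 describes mostly mild events without apparent dose-response, and its further sentence, "instillation site erythema, blurred vision, and muscle strain were reported in 3 subjects at moderated intensity", includes a non-ocular event.

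Two more points are fair. Exclusion 15 concerns history before Screening, and prostaglandin users then wash out for at least 6 weeks, so it does not show how often the graded baseline is abnormal. Table layouts sit in a separate document (SAP 6), so further tables may exist, but the SAP does not commit to them.

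**Conclusion.** The point holds in a limited form. SAP 4.12.4 does not use the baseline defined in 4.1, so the number of subjects per regimen who worsened on slit lamp cannot be derived from the planned tables. SAP 4.12.5 cannot give the number who ever reached a given hyperemia grade. Rises such as 0.5 to 2 or 1 to 2 that are judged not clinically significant may also be absent from the AE tables. The fundus part is weak: Day 28 is the only scheduled post-dose examination, and deterioration is already an AE.

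The size is unknown. The illustrations (0 to 10 new slit-lamp cases behind equal counts of 10 in 50; 10% to 57% ever affected behind 10% at each of 8 readings) show what the tables leave open, not what is expected. No hypothesis test or data collection is affected. It is a descriptive gap in the secondary objective and is worth closing because it costs little.

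**What to change.** - **SAP 4.12.4:** add a shift table from the 4.1 baseline to the worst post-dose category, per subject and eye, by treatment group.
- **SAP 4.12.5:** add, per subject and eye, the worst post-dose grade and the largest increase from time-matched baseline. Give the number and percentage at each level in the Safety population, with the Clopper-Pearson 95% CI already used elsewhere in the SAP.
- **Readings:** base the main summary on the protocol-scheduled readings without +12 h, so that arms and subjects are comparable. Give a second version that adds unscheduled and Early Termination readings, with a time-matched baseline where one exists.
- **SAP 4.12.6:** a simple shift from baseline to Day 28 is enough and has low priority.
- **Reconcile:** Protocol 5.1.4 lists hyperemia grading on Days 7 and 14, while Table 1 shows none on Day 7. The answer changes the count of readings from 8 to 9.

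The cost is SAP wording and a few tables before database lock, with no new data, visits or protocol amendment for the tables. The downside is that a worst grade is sensitive to a single high grading and rises with the number of readings. At an assumed 10% with independence, 8 readings give 57% and 10 readings give 1 − 0.9^10 = 65%. The summary should therefore be read beside the tables by time point, which stay.

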4.12.5 Conjunctival Hyperemia Grading

The number and percentage of subjects within each grading category will be summarized by treatment group, visit, timepoint and eye. In addition, shift from baseline will be summarized by treatment group, visit, timepoint and eye (study eye and fellow eye).

4.12.6 Dilated Ophthalmoscopy

The number and percentage of subjects within each assessment category will be summarized by treatment group, visit and eye (study eye and fellow eye).

4.13 Subgroup Analysis

No subgroup analyses will be performed.

30-Jan-24

4.14 Interim Analysis

No interim analysis is planned.

5 Summary of Changes from the Protocol

The sample size section of the protocol refers to a non-inferiority limit of 2, while the thresholds of 1.5 and 1 will be used in the analysis of the primary endpoint.

In the protocol, the primary endpoint refers to Day 28 only. In the SAP, the primary endpoint is concluded as non-inferior based on the 5 time points at Day 28 and the 4 on-treatment time points at Day 1.

6 List of Programming Summary & Analysis Tables

Confidential

The list and layout of the summary tables and listings will be described in a separate document.

7 Appendices

Assessments/Procedures ¹	Screening (-49 to 1 days)	Day 0 (-4 to -1)	Day 1 Baseline/Randomization	Day 7 (± 1 day)	Day 14 (± 1 day)	Day 28 (± 2 days) Last Dosing Day
	Visit 1	Visit 2	Visit 3	Visit 4	Visit 5	Visit 6
Intraocular Pressure ⁴ (Goldmann Tonometry)	X	X Pre-T ₀ T ₀ + 2 hrs T ₀ + 4 hrs T ₀ + 8 hrs T ₀ + 12 hrs ³	X Pre-T ₀ $T_0 + 2 \text{ hrs}$ $T_0 + 4 \text{ hrs}$ $T_0 + 8 \text{ hrs}$ $T_0 + 12 \text{ hrs}^3$	X Pre-T ₀	X Pre-T ₀	X Pre-T ₀ $T_0 + 2 \text{ hrs}$ $T_0 + 4 \text{ hrs}$ $T_0 + 8 \text{ hrs}$ $T_0 + 12 \text{ hrs}^3$
Gonioscopy ⁵	X					
Pachymetry ⁶	X					
Visual Fields (automated, threshold) ⁷	X					
Ophthalmoscopy (dilated)	X					X

Version 2.0 Final Z-estima Ltd.

Page 19 of 19

30-Jan-24

⁴ Timing of IOP measurements for each subject should be consistent throughout the study. Calculate timepoints in relation to T₀: timepoints +2 and +4 hrs after T₀ must be separated from the prior timepoint by at least 1½ hrs and timepoints +8 and +12 hrs must be separated from the prior timepoint by at least 3½ hours. Every effort should be made to conduct Visit 6 Day 28 Pre-T₀ and In-Office IP Administration (AM dose) at the identical time as done on Visit 3 Day 1.

⁵ Gonioscopy within 6 months of Screening acceptable.

⁶ Pachymetry performed at screening will be used for inclusion/exclusion criteria only. Pachymetry within 6 months of Screening acceptable.

⁷ Reliable visual fields within 6 months of Screening acceptable.
